### Clinical Studies:

All clinical studies to determine eligibility must be performed within 7 days prior to enrollment unless otherwise indicated. Imaging studies, bone marrow biopsy and/or aspirate, biopsy of extramedullary site (if the bone marrow is not involved by disease) and lumbar puncture must be obtained within 14 days prior to enrollment (repeat the tumor imaging if necessary).

Clarification in timing when counting days: As an example, please note that if the patient's last day of prior therapy is September 1st, and the protocol requires waiting at least 7 days for that type of prior therapy, then that patient cannot be enrolled until September 8th.

## 4.1 Inclusion Criteria

4.1.1 Patient must be enrolled on APAL2020SC - Pediatric Acute Leukemia (PedAL) Screening Trial – Developing New Therapies for Relapsed Leukemias - A Leukemia & Lymphoma Society and COG Groupwide Screening Protocol.

### 4.1.2 Age

Patients must be  $\geq 1$  year and  $< 18$  years of age at the time of study enrollment.

### 4.1.3 Diagnosis

Patients, with or without Down syndrome (DS), and with *de novo* acute myeloid leukemia, therapy-related acute myeloid leukemia, myelodysplastic syndrome with increased blasts (MDS-IB), therapy-related myelodysplastic syndrome with increased blasts (MDS-IB) or mixed phenotype acute leukemia that expresses E-selectin ligand on the cell membrane according to APAL2020SC screening results and meet one of the following:

- Second or greater relapse or refractory AML as defined below, including isolated extramedullary disease (EMD), but excluding isolated central nervous system (CNS) or isolated testicular disease.
- Second or greater relapse or refractory myelodysplastic syndrome (MDS) with increased blasts (MDS-IB).

THIS PROTOCOL IS FOR RESEARCH PURPOSES ONLY, SEE PAGE 1 FOR USAGE POLICY

- Second or greater relapse or refractory mixed phenotype acute leukemia (MPAL).

**Note:** Documentation of E-selectin expression by multidimensional flow cytometry (MDF) at the central laboratory (Hematologics, Inc.) on the most recent bone marrow sample prior to the diagnosis of the current relapsed or refractory disease is acceptable for eligibility to this study in the event of isolated extramedullary disease, inability to obtain a bone marrow aspirate or lack of leukemic blasts in the peripheral blood.

#### 4.1.4 Disease Status

##### 4.1.4.1 *Bone marrow relapse and MDF – MRD relapse:*

(patients must meet one of the following criteria to be defined as having relapse disease)

- A single bone marrow sample showing  $\geq 1\%$  leukemic blasts by multidimensional flow cytometry performed at the central laboratory (performed only at Hematologics through the screening study APAL2020SC).
- In cases where a bone marrow aspirate cannot be obtained because of extensive fibrosis, blast count can be obtained from touch imprints or estimated from an adequate bone marrow core biopsy; blast count must be  $\geq 5\%$  to be eligible. A complete blood count documenting the presence of at least 1,000/ $\mu\text{L}$  (i.e., a WBC count  $\geq 10,000/\mu\text{L}$  with  $\geq 10\%$  blasts or a WBC count of  $\geq 5,000/\mu\text{L}$  with  $\geq 20\%$  blasts) circulating leukemic cells (blasts) can also be used if a bone marrow aspirate or biopsy cannot be performed.

##### 4.1.4.2 *Extramedullary relapse:*

Biopsy proven extramedullary disease after documented complete remission.

##### 4.1.4.3 *Refractory disease and MDF – MRD refractory:*

Following a re-induction cycle after any relapse, presence of  $\geq 1\%$  leukemic blasts by multidimensional flow cytometry performed at the central laboratory (performed only at Hematologics through the screening study APAL2020SC), OR there is persistent extramedullary disease. In cases where a bone marrow aspirate cannot be obtained because of extensive fibrosis, assessment of refractory disease will be defined as described above in 4.1.4.1 II.

#### 4.1.5 Therapeutic Options

Patient's current disease state must be one for which there is no known curative therapy or therapy proven to prolong survival with an acceptable quality of life.

#### 4.1.6 Performance Level

Karnofsky  $\geq 50$  for patients  $> 16$  years of age and Lansky  $\geq 50$  for patients  $\leq 16$  years of age.

Patients must have a performance status corresponding to ECOG scores of 0, 1 or 2. Use Karnofsky for patients  $> 16$  years of age and Lansky for patients  $\leq 16$  years of age.

See [https://www.cogmembers.org/site/pages/default.aspx?page=Prot\\_reference\\_materials](https://www.cogmembers.org/site/pages/default.aspx?page=Prot_reference_materials) under Standard Sections for Protocols.

#### 4.1.7 Prior Therapy

4.1.7.1 Patients must have fully recovered (grade <2) from the acute toxic effects of all prior anti-cancer therapy and must meet the following minimum duration from prior anti-cancer directed therapy prior to enrollment. If after the required timeframe, the numerical eligibility criteria are met, eg, blood count criteria, the patient is considered to have recovered adequately.

a. Cytotoxic chemotherapy or other anti-cancer agents known to be myelosuppressive: See DVL homepage on the COG Members site for commercial and investigational agent classifications. For agents not listed, the duration of this interval must be discussed with the study chair and the study-assigned Research Coordinator prior to enrollment.

- $\geq 14$  days must have elapsed after the completion of other cytotoxic therapy, with the exception of hydroxyurea.

**NOTE:** Cytorreduction with hydroxyurea must be discontinued  $\geq 24$  hours prior to the start of protocol therapy.

b. Anti-cancer agents not known to be myelosuppressive (eg, not associated with reduced platelet or ANC counts):  $\geq 7$  days after the last dose of agent. See the DVL homepage on the COG Members site for commercial and investigational agent classifications. For agents not listed, the duration of this interval must be discussed with the study chair and the study-assigned Research Coordinator prior to enrollment.

c. Antibodies:  $\geq 21$  days must have elapsed from infusion of last dose of antibody, and toxicity related to prior antibody therapy must be recovered to Grade  $\leq 1$ .

d. Corticosteroids: See [Section 4.2.3.1](#). If used to modify **immune adverse events** related to prior therapy,  $\geq 14$  days must have elapsed since last dose of corticosteroid.

e. Hematopoietic growth factors:  $\geq 14$  days after the last dose of a long-acting growth factor (e.g., pegfilgrastim) or 7 days for short-acting growth factor. For agents that have known adverse events occurring beyond 7 days after administration, this period must be extended beyond the time during which adverse events are known to occur.

f. Interleukins, Interferons and Cytokines (other than Hematopoietic Growth Factors):  $\geq 21$  days after the completion of interleukins, interferon or cytokines (other than Hematopoietic Growth Factors)

g. Stem cell Infusions (with or without TBI):

- Allogeneic (non-autologous) bone marrow or stem cell transplant, or any stem cell infusion including DLI or boost infusion:  $\geq 84$  days after infusion and no evidence of GVHD.
- Patients must be off calcineurin inhibitors for at least 28 days prior to the start of protocol therapy. Patients may be on physiological doses of steroids (equivalent to  $\leq 10$  mg prednisone daily for patients  $\geq 18$  years or  $\leq 10$  mg/m^2/day for patients <18 years).
- Autologous stem cell infusion including boost infusion:  $\geq 30$  days.

THIS PROTOCOL IS FOR RESEARCH PURPOSES ONLY, SEE PAGE 1 FOR USAGE POLICY

- h. Cellular Therapy:  $\geq 30$  days after the completion of any type of cellular therapy (eg, modified T cells, NK cells, dendritic cells, etc.).
- i. XRT/External Beam Irradiation including Protons:  $\geq 14$  days after local XRT;  $\geq 150$  days after TBI, craniospinal XRT or if radiation to  $\geq 50\%$  of the pelvis;  $\geq 42$  days if other substantial BM radiation.
- j. Patients must not have received prior exposure to uproleselan (GMI-1271). NOTE: Prior therapy with fludarabine and/or cytarabine is permitted.

#### 4.1.8 Organ Function Requirements

##### 4.1.8.1 Adequate Bone Marrow Function Defined As:

- a. For patients with leukemia:
  - Platelet count  $\geq 25,000/\mu\text{L}$  (may receive platelet transfusions).

##### 4.1.8.2 Adequate Renal Function Defined as:

- 1) Estimated GFR (eGFR)  $\geq 70 \text{ mL/min/1.73 m}^2$   
"Bedside" Schwartz formula (2009):  
 $eGFR = 0.413 \times (\text{height (cm)} / \text{serum creatinine (mg/dL)})$

An online calculator is available through the National Kidney Foundation at  
[https://www.kidney.org/professionals/kdoqi/gfr\\_calculatorped](https://www.kidney.org/professionals/kdoqi/gfr_calculatorped)

OR

- 2) Measured GFR  $\geq 70 \text{ mL/min/1.73 m}^2$ . If *measured GFR* is used, it must be performed using direct measurement with a nuclear blood sampling method or small molecule clearance method (iothalamate or other molecule per institutional standard).

##### 4.1.8.3 Adequate Liver Function Defined as:

- Bilirubin (sum of conjugated + unconjugated)  $\leq 1.5 \times$  upper limit of normal (ULN) for age.
- SGPT (ALT)  $< 3 \times$  ULN (unless attributed to leukemic involvement).
- Albumin  $\geq 2 \text{ g/dL}$ .

##### 4.1.8.4 Adequate Cardiac Function Defined as:

- Shortening fraction of  $\geq 27\%$  by echocardiogram, or
- Ejection fraction of  $\geq 50\%$  by gated radionuclide study.

## 4.2 **Exclusion Criteria**

### 4.2.1 Patients with any of the following diagnoses

- Patients with isolated relapsed or refractory CNS disease or isolated relapsed or refractory testicular disease
- Patients with acute promyelocytic leukemia (APL)
- Patients with juvenile myelomonocytic leukemia (JMML)
- Patients with a known congenital bone marrow failure syndrome

### 4.2.2 Pregnancy or Breast-Feeding

Pregnant or breast-feeding women will not be entered on this study due to risks of fetal and teratogenic adverse events as seen in animal/human studies, OR because there is yet no available

THIS PROTOCOL IS FOR RESEARCH PURPOSES ONLY, SEE PAGE 1 FOR USAGE POLICY

information regarding human fetal or teratogenic toxicities. Pregnancy tests must be obtained in girls who are post-menarchal. Males or females of reproductive potential may not participate unless they have agreed to use two effective methods of birth control, including a medically accepted barrier or contraceptive method (eg, male or female condom) for the duration of the study and for 3 months after the last dose of uproleselan (GMI-1271). Abstinence is an acceptable method of birth control.

#### 4.2.3 Concomitant Medications

4.2.3.1 Corticosteroids: Patients receiving corticosteroids who have not been on a stable or decreasing dose of corticosteroid for at least 7 days prior to enrollment are not eligible. If used to modify **immune adverse events** related to prior therapy,  $\geq 14$  days must have elapsed since last dose of corticosteroid (see [Section 4.1.7.1.d](#)).

4.2.3.2 Investigational Drugs: Patients who are currently receiving another investigational drug are not eligible.

4.2.3.3 Anti-cancer Agents: Patients who are currently receiving other anti-cancer agents are not eligible except patients receiving hydroxyurea, which may be continued until 24 hours prior to start of protocol therapy.

4.2.3.4 Anti-GVHD Agents Post-transplant: Patients who are receiving cyclosporine, tacrolimus or other agents to prevent graft-versus-host disease post bone marrow transplant are not eligible for this trial.

#### 4.2.4 Infection

Patients who have an uncontrolled infection are not eligible.

4.2.5 Patients who have received a prior solid organ transplantation are not eligible.

4.2.6 Patients who in the opinion of the investigator may not be able to comply with the safety monitoring requirements of the study are not eligible.

### 4.3 CNS Status Definition

#### CNS1 Disease

CNS1 (negative) at diagnosis of relapsed/refractory disease is defined as no blasts in cytospin CSF regardless of CSF WBC or RBC counts **AND** no clinical signs of CNS leukemia (such as facial nerve palsy, brain/eye involvement or hypothalamic syndrome) **AND** no radiographic evidence of intracranial or intradural mass.

#### CNS2 Disease

CNS2 disease at diagnosis of relapsed/refractory disease is defined as blasts present in cytospin CSF with CSF WBC  $< 5/\mu\text{L}$ .

#### CNS3 Disease

CNS3 disease at diagnosis of relapsed/refractory disease is defined as blasts present in cytospin CSF with CSF WBC  $\geq 5/\mu\text{L}$  **AND/OR** clinical signs of CNS leukemia (such as facial nerve palsy, brain/eye involvement or hypothalamic syndrome) **OR** radiographic evidence of an intracranial or intradural mass consistent with a chloroma. Retinal hemorrhage and extra-ocular orbital masses are not considered CNS leukemia.

## 5.0 TREATMENT PLAN

### 5.1 Overview of Treatment Plan

**Table 2 – Experimental Design Schema**

Each Cycle (28 days)						
	Uproleselan (GMI-1271) IV	Fludarabine IV	Cytarabine IV	Cytarabine IT	IT Triples	Leucovorin PO or IV
Day 0				once daily 	once daily 	
Day 1	once daily					24 and 30hrs post ITT 
Day 2	q12hr	once daily	once daily			
Day 3	q12hr	once daily	once daily			
Day 4	q12hr	once daily	once daily			
Day 5	q12hr	once daily	once daily			
Day 6	q12hr	once daily	once daily			
Day 7	q12hr			Weekly 	Weekly 	
Day 8	q12hr					24 and 30hrs post ITT 
Day 9						
...						
Day 14				Weekly 	Weekly 	
Day 15						24 and 30hrs post ITT 
Day 21				Weekly 	Weekly 	
Day 22						24 and 30hrs post ITT 
Day 28				Weekly 	Weekly 	
Day 29 						24 and 30hrs post ITT 

 Choice between IT Cytarabine OR IT Triples is up to the treating physician's discretion. Weekly intrathecal chemotherapy treatments are for CNS 2/3 patients ONLY. A minimum of 4 and a maximum of 6 intrathecal treatments may be given (count includes day 0 IT and may carry over into Cycle 2 of chemotherapy).

 Down syndrome patients ONLY. Administer 24 & 30 hours after each IT Triples.

 End of cycle bone marrow for disease assessment may be performed any day between Day 28-35.

 Day 28 lumbar puncture can be done at the same time as the end of cycle bone marrow assessment between day 28-35.

A cycle of therapy is considered to be 28 days. A cycle may be repeated for a total of 2 cycles, up to a total duration of therapy of approximately 2 months.

Drug doses of uproleselan (GMI-1271) should be adjusted based on the weight measured within 7 days prior to the beginning of each cycle. Drug doses of fludarabine and cytarabine should be adjusted based on the BSA (calculated from the height and weight) or weight (patients < 1 year) measured within 7 days prior to the beginning of each cycle. Drug doses of intrathecal cytarabine, methotrexate and hydrocortisone should be based on the age of the patient at the time of administration.

THIS PROTOCOL IS FOR RESEARCH PURPOSES ONLY, SEE PAGE 1 FOR USAGE POLICY

See [Section 5.6](#) for Therapy Delivery Maps for each cycle. Additional IT cytarabine or IT triples will be administered for CNS2 and CNS3 patients weekly according to the schedule in the Therapy Deliver Maps in [Section 5.6](#).

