#### **5.1.4 Intrathecal Therapy: IT**

CNS 1 patients: Day 0 and 28

CNS 2/3 patients: Days 0, 7, 14, 21, 28

All patients will receive intrathecal therapy with either IT cytarabine ([Section 5.1.4.1](#)) or triple intrathecals with methotrexate/hydrocortisone/cytarabine (ITT) ([Section 5.1.4.2](#)) in this study according to the schedule above. The choice between IT cytarabine vs triple IT therapy is up to the treating physician's discretion.

Patients will receive a single dose of IT cytarabine or ITT on Day 0 of Cycle 1. It is recommended, but not required, that systemic therapy with uproleselan (GMI-1271) begin at least 24 hours after the intrathecal therapy.

If the patient received IT cytarabine or triple IT therapy during their diagnostic workup within 14 days of starting protocol therapy, then they do not need additional Day 0 IT therapy.

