### 5.5.2.2 **Note:** Grade 3 or 4 febrile neutropenia will not be considered a dose-limiting toxicity.

## 5.6: THERAPY DELIVERY MAPS (TDMS) FOR CYCLE 1-2

**Therapy Delivery Map – Cycle 1-2** A cycle of therapy is considered to be 28 days. A cycle may be repeated for a total of 2 cycles, up to a total duration of therapy of approximately 2 months. Refer to [section 4.1](#) for eligibility criteria to start cycle 1. For patients in MRD negative remission, it is required that patients have an ANC >200/ $\mu$ L or a sustained platelet count >20,000/ $\mu$ L before proceeding with cycle 2.

This form is to be completed and uploaded into RAVE at the end of every cycle.

Accession #

Patient COG ID number

Institution

Extensive details are in [Section 5.1](#) (treatment overview). This TDM extends to three pages.

DRUG	ROUTE	DOSAGE	DAYS	IMPORTANT NOTES																				
IT Cytarabine (AraC)	Intrathecal (IT)	Age-based dosing: 

Age	Dose	

< 1 year	20 mg	

≥ 1 to < 2 years	30 mg	

≥ 2 to < 3 years	50 mg	

≥ 3 years	70 mg	

	Age	Dose	< 1 year	20 mg	≥ 1 to < 2 years	30 mg	≥ 2 to < 3 years	50 mg	≥ 3 years	70 mg	Days 0 ^ , 7*, 14*, 21*, 28 ^	
^All patients. First time point given at the time of diagnostic lumbar puncture OR Day 0 for all patients. Note that Day 28 LP with IT chemotherapy of Cycle 1 counts as Day 0 LP with IT of Cycle 2. If the patient received IT cytarabine or triple IT therapy during their diagnostic workup within 14 days of starting protocol therapy, then they do not need additional Day 0 IT therapy.
 
*CNS 2/3 patients ONLY.
 
A minimum of 4 and a maximum of 6 weekly (count includes day 0 IT) intrathecal treatments may be given. The choice between IT Cytarabine OR IT Triples is up to the treating physician's discretion. See Section 5.1 for administration guidelines.
										
Age	Dose																							
< 1 year	20 mg																							
≥ 1 to < 2 years	30 mg																							
≥ 2 to < 3 years	50 mg																							
≥ 3 years	70 mg																							

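### Tables 1 and 2 restrict Day 28 intrathecal therapy to CNS2/3 patients, while Section 5.1.4 and the delivery map also schedule it for CNS1 patients

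*Combined protocol and SAP*

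**What the plan says.** Tables 1 and 2 are the same schema printed twice. Day 0 is labelled once daily in both intrathecal columns. Days 7, 14, 21 and 28 are all labelled Weekly. All of these cells carry footnote 1, which states: "Weekly intrathecal chemotherapy treatments are for CNS 2/3 patients ONLY". The only other remark on Day 28 intrathecal timing is footnote 4: "Day 28 lumbar puncture can be done at the same time as the end of cycle bone marrow assessment between day 28-35". It names no CNS group.

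Section 5.1.4 gives a schedule by CNS status. Its first line is "CNS 1 patients: Day 0 and 28", and CNS2/3 patients have Days 0, 7, 14, 21 and 28. It adds that "All patients will receive intrathecal therapy with either IT cytarabine" or triple intrathecal therapy, following that schedule. Sections 5.1.4.1 and 5.1.4.2 repeat the CNS1 days for each regimen.

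The delivery map in Section 5.6 uses two markers. The asterisk, on Days 7, 14 and 21, means CNS2/3 only. The caret, on Days 0 and 28, is explained as "All patients. First time point given at the time of diagnostic lumbar puncture OR Day 0 for all patients". The map's day-by-day grid carries the caret in its Day 28 row too. The map also says: "Note that Day 28 LP with IT chemotherapy of Cycle 1 counts as Day 0 LP with IT of Cycle 2".

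**The concern.** Intrathecal therapy is part of protocol therapy. A reader working from either schema table would conclude that a CNS1 patient has no intrathecal dose on Day 28. A reader working from Section 5.1.4 or the map would schedule one. Leucovorin on Day 29 for Down syndrome patients on triple therapy (Section 5.1.5) follows from the same decision.

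Aim 1.1.3 is to describe the toxicities of the combination. If CNS1 patients were managed from different pages, that description would pool patients with different scheduled intrathecal exposure, and the protocol would give no single rule for saying who had been treated as planned.

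**Working it through.** The protocol states no total number of intrathecal doses for a CNS1 patient, so there is no figure to reproduce. The check compares the sections and counts scheduled doses by hand.

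**Day 28 rule in each place**

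| Place | Day 28 marking | CNS1 patient on Day 28 |
|---|---|---|
| Table 1 (Experimental Design Schema) | Weekly, footnote 1 | No dose |
| Table 2 (Section 5.1) | Weekly, footnote 1 | No dose |
| Section 5.1.4 | CNS1 days listed as 0 and 28 | Dose |
| Sections 5.1.4.1 and 5.1.4.2 | CNS1 days listed as 0 and 28 | Dose |
| Section 5.6, drug rows and daily grid | Caret (all patients) | Dose |

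In the tables, Day 28 is labelled exactly like Days 7, 14 and 21. Only Day 0 is labelled differently. So the tables give no ground for treating Day 28 as an exception to footnote 1.

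**Cycle 1 count, CNS1 patient**

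- Tables: Day 0 = 1 dose.
- Section 5.1.4 and map: Day 0 + Day 28 = 2 doses.
- Difference: 2 − 1 = 1 dose.

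If the Day 0 dose is waived because intrathecal therapy was given in the diagnostic workup within 14 days of starting protocol therapy (Section 5.1.4), each count falls by one, to 0 and 1. The difference is still 1 dose.

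**Two-cycle count, CNS1 patient (no waiver)**

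- Section 5.1.4 and map: Cycle 1 Day 0, Cycle 1 Day 28 (credited as Cycle 2 Day 0), Cycle 2 Day 28 = 3 doses.
- Tables, with the Each Cycle header applied to Day 0: 1 + 1 = 2 doses. Difference: 3 − 2 = 1.
- Tables, with Day 0 taken as Cycle 1 only, as Section 5.1.4 words it: 1 dose. Difference: 3 − 1 = 2.

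The two-cycle difference is therefore 1 or 2 doses, depending on the reading.

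**Does anything settle the conflict?** Footnote 4 deals with the timing of the puncture and does not lift footnote 1. The cross-reference after Table 2 sends readers to the maps for the additional weekly CNS2/3 doses, not for the CNS1 rule. No order of precedence is stated. Both tables are current text, and the summary of changes records only that they were given table labels.

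**DLT window.** DLT is observed in the first cycle (Section 5.5), a cycle is 28 days, and the Day 28 dose may be given on Days 28 to 35. Section 6.3.1.2 says methotrexate leukoencephalopathy often appears 1 to 2 weeks after an intrathecal dose. That is from Day 28 + 7 = 35 to Day 35 + 14 = 49, after the nominal cycle end.

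**The case against.** The strongest reply is that the operative instructions agree. Section 5.1.4, both subsections and the map's day markers give the same CNS1 schedule, and the map is the form that sites must complete and upload every cycle. The tables are overviews. This stands and limits the practical effect. It does not remove the conflict, because the tables are part of the treatment plan. The map's closing note, which describes the choice of regimen for Day 0 and then for later days in CNS2 and CNS3 patients, can even be read the tables' way.

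It can also be said that footnote 4 foresees a Day 28 puncture without restricting it. I found no anchor for that footnote in either table, and a superscript lost in text conversion cannot be excluded. Even anchored to Day 28, it would address timing only.

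Three stronger inferences are tempting, and the documents do not support them:

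- A reader might infer that lumbar punctures and end-of-cycle CSF samples would differ. Item m of the map's required observations asks for CSF at the end of Cycles 1 and 2 without regard to CNS status, and the Day 28 row lists it. The open question is whether drug is given.
- A reader might infer a second contradiction over Day 0 of Cycle 2, because the tables are headed Each Cycle. The map's crediting note explains how that Day 0 dose is met.
- A reader might infer that DLT counts, and so the MTD decision, are at risk. The dose falls at or after the nominal end of Cycle 1. A narrow route remains through Section 5.5.1.2, where non-hematological toxicity delaying the next cycle by 14 days or more is a DLT, but no dose-finding rule or sample size depends on the Day 28 cell.

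**Conclusion.** This is a real internal contradiction, minor in weight. Tables 1 and 2, as printed, exclude CNS1 patients from Day 28 intrathecal therapy; Section 5.1.4, its subsections and the delivery map include them. The size is one scheduled dose per CNS1 patient in Cycle 1, whether or not the Day 0 dose is waived.

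The conclusion rests on reading the Weekly label and footnote 1 literally. A reader might infer that every CNS1 patient is affected or that sites will in fact differ. The documents show neither, since a site filling in the map would probably follow Section 5.1.4. What can be said is that a difference in intrathecal exposure is possible, and that it would touch the toxicity description in aim 1.1.3. No extra analysis is called for, because the uploaded map already records each dose given.

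**What to change.** Reconcile the Day 28 intrathecal cells and footnote 1 in Tables 1 and 2 with Sections 5.1.4, 5.1.4.1 and 5.1.4.2 and the delivery map, so that one Day 28 rule for CNS1 patients appears in every place. Which schedule applies is for the study committee to decide. While editing, confirm where footnote 4 is anchored and that the Day 29 leucovorin row agrees with the rule chosen.

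If only the tables change, the cost is an edit to one row and one footnote, each printed twice, in the next amendment. If the committee settles on the tables' reading, Section 5.1.4, its two subsections and the map markers need the matching edit. Neither route changes the sample size, the DLT definition or the dose-finding rules.
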